4.0. Human Subjects

4.1 General Characteristics – Minority Inclusion and Non-Discriminatory Statements.

Because this study evaluates pregnancy in von Willebrand disease, only females \geq 18 years of age will be included in this study: males and children are excluded. VWD will be defined as VWF:RCo < 0.50 IU/dL (historic) and previous history of bleeding. The racial, gender, and ethnic characteristics of the proposed subject population reflects the demographics of Pittsburgh and the surrounding area and/or the patient population of the University of Pittsburgh Medical Center. Subjects will be recruited in proportion to these demographics. No exclusion criteria shall be based on race or ethnicity.

4.2 Inclusion of Children

Because the study is undertaken to study pregnancy, children are excluded from study.

4.3 Inclusion/ Exclusion Criteria

Inclusion Criteria will include:

1. Pregnant females \geq 18 years of age
2. Confirmed VWD, as defined by VWF:RCo < 0.50 IU/dL and previous history of bleeding
3. Willingness to have blood drawn
4. Willing to be randomized to one of two treatments at delivery and for 2 days postpartum.
5. Willing to keep a diary for 3 weeks of postpartum bleeding by pictorial assessment chart (PBAC) and any blood products, transfusion, or medications taken.
6. Willing to return at 21 days for final blood draw and review of diary.

Exclusion Criteria will include:

1. Any bleeding disorder other than VWD; or past thrombotic disease of other bleeding disorders.
2. Previous thrombosis, cardiac disease, congestive failure, arrhythmia, hypertension, MI, or stroke.
3. Platelet count $< 100,000/\text{ul}$.
4. Past allergic reaction to VWF or tranexamic acid.
5. Surgery within the past 8 weeks.
6. Inability to comply with study protocol requirements.
7. Concomitant use of antiplatelet drugs, anticoagulants, or NSAIDs. Aspirin will be allowed for preeclampsia prevention.
8. Treatment with DDAVP, cryoprecipitate, whole blood, plasma or plasma derivatives containing substantial quantities of VWF within 5 days of study.
9. History of renal disease.
10. Inability to comply with study requirements.

Risk/Benefit Assessment: This research involves pregnant women, and thus children are excluded. Among adults, there is some risk with blood draw, but there remains the potential for direct individual benefit. This is based on the balance in favor of potential benefit from receiving a potentially more effective treatment, VWF+TA, over the standard treatment, rVWF alone, with potential risk associated with blood drawing and potential, but rare expected adverse reactions (see below).

4.4 Sources of Research Material. Plasma for all laboratory testing will be collected from subjects enrolled on the study.

4.5 Recruitment Methods and Consent Procedures. It is estimated that 20 subjects will be enrolled at this study site. Pregnant females \geq age 18 years of age with VWD, defined by VWF:RCO < 0.50 IU/dL (historic) and a previous bleeding history, who fulfill the inclusion and exclusion criteria, and who are cared for at HCWP or Magee outpatient clinic (Pilot Study) or one of the approximately 19 HTCs/obstetric hospitals (Phase III trial) participating in this trial *will be eligible for study*. Subjects approached for participation in this study will have VWD and be contacted during routine clinic visits to determine their interest in participating in the study.

Demographic Chart: Targeted Enrollment for Pilot Study

TARGETED/PLANNED ENROLLMENT: Number of Subjects			
Ethnic Category	Sex/Gender		
	Females	Males	Total
Hispanic or Latino	1	0	1
Not Hispanic or Latino	19	0	19
Ethnic Category: Total of All Subjects *	20	0	20
Racial Categories			
American Indian/Alaska Native	0	0	0
Asian	0	0	0
Native Hawaiian or Other Pacific Islander	0	0	0
Black or African American	1	0	1
White	19	0	19
Racial Categories: Total of All Subjects *	20	0	20

* The “Ethnic Category: Total of All Subjects” must be equal to the “Racial Categories: Total of All Subjects.”

There will be no cold calling. The Site PI will determine the patient’s interest in study participation, and, if the patient is interested, the study will be discussed in further detail and the informed consent reviewed. Subjects will be encouraged to take time to decide on participation and ask questions. If subjects decide to take a consent form home for further viewing, discussion will include the purpose, safety issues, and risks and benefits of the study. All questions will be answered prior to and obtaining informed consent. No experimental procedures or interventions will occur until after informed consent is obtained. The investigator’s certification statement will be signed at the time consent is obtained. If any new information occurs during the conduct of the study, subjects who have been consented will be informed and will be re-consented with this information at the next visit. A de-identified prescreening/ screening log will be kept, and all reasons for exclusion documented in study source documents and screening log. Subjects who read the consent form are free to refuse enrollment, and participants will be free to withdraw at any time. If subjects wish to withdraw, they may do so by addressing a letter to the principal investigator. Any data collected prior to the time of withdrawal will continue to be used, but no additional information will be collected. Processed blood sample results will continue to be used for the research study; however, remaining samples will be destroyed or used as indicated by subject’s letter. The reason (e.g. AE, lost to follow-up, etc.) and date of withdrawal for all subjects withdrawn from this study will be recorded. Subject information obtained by electronic data capture will be stored and managed on the GSPH Data Center website. The IRB may inspect the records of this study. Every effort will be made to keep the subject’s personal medical data confidential.

Subject eligibility for the study will be determined prior to randomization and the first dose of rVWF and/or TA. Subjects will sign informed consent. Subject screening and enrollment will be conducted by the local Investigator, in communication with the GSPH Data Center web-based data entry system. Subjects will be considered to be enrolled in the study after all assessments have been completed during the Screening period. No subject may receive treatment prior to enrollment and assignment of a unique subject identification number. Any subject identification numbers that are assigned will not be reused even if the subject does not receive treatment.

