This is a prospective, randomized single-center phase III pilot clinical trial comparing recombinant von Willebrand factor (rVWF, Vonvendi®) plus tranexamic acid (TA, Cyclokapron®) vs. rVWF alone to reduce postpartum hemorrhage (PPH) in women with von Willebrand disease (VWD). We *hypothesize* that intravenous rVWF given just before delivery plus intravenous tranexamic acid within 3 hours of delivery is superior to rVWF alone in reducing postpartum blood loss.

Objective:

The **Primary Objective** is to determine the efficacy of rVWF plus TA vs. rVWF alone in reducing postpartum hemorrhage in women with VWD.

The **Secondary Objectives** are to evaluate safety, tolerability, and mechanism of rVWF plus TA vs. rVWF alone in reducing PPH in women with VWD.

Endpoints:

The **Primary Endpoint** is quantitative blood loss (QBL) calculated by a labor suite nurse at delivery. The **Secondary Endpoints** include safety assessment by lochial blood loss by pictorial blood assessment chart (PBAC), blood products, transfusion, and hysterectomy within 21 days of delivery; and mechanism of PPH reduction by VWF assays, fibrinogen, and d-dimer.

Study Population:

Study subjects will be females age \geq 18 years of age with von Willebrand disease, defined by VWF:RCo <0.50 IU/dL (historic) and previous bleeding history, undergoing vaginal or caesarean section delivery. A total of 20 eligible subjects with VWD will be enrolled in this 2-year trial.

Site Enrolling Subjects:

Pilot: Participating site is HCWP, and Magee Hospital obstetricians.

Description of Study Intervention:

There are two study interventions: rVWF plus tranexamic acid vs. rVWF alone. Recombinant von Willebrand factor (rVWF, Vonvendi®) is an FDA-approved clotting factor approved for treatment or prevention of bleeds including postpartum hemorrhage hemorrhage in VWD. It is an intravenous agent administered in single-use vials containing approximately 650-1300 IU per vial as a sterile, lyophilized powder. The vials are reconstituted with 5-10 ml vial of sterile water for injection, USP, which is transferred by two-way needle into the lyophilized powder for reconstitution, and the reconstituted vial infused over 5-10 minutes, at 80 IU/kg (per pre-pregnancy weight) at delivery (or epidural), and days 1 and 2 postpartum.

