This is a single-center randomized phase III pilot clinical trial, the **VWD-Woman Trial**, in which 20 pregnant women with von Willebrand disease, defined as VWF:RCo <0.50 IU/ml (historic) and previous bleeding history, are enrolled. Subjects will include women with VWD age 18 years of age and older, excluding those who have a bleeding disorder other than VWD. Once enrolled, subjects who meet all of the inclusion and none of the exclusion criteria will be randomized to recombinant Von Willebrand factor (Vonvendi, rVWF[®]) with Tranexamic Acid (TA, cyclokapron[®]) or recombinant Von Willebrand factor (Vonvendi, rVWF[®]) alone to prevent postpartum hemorrhage after a vaginal or caesarean section. The primary endpoint is quantitative blood loss (QBL) collected by a labor suite nurse at delivery, and secondary endpoints include safety assessment for postpartum lochial blood loss by Pictorial Blood Assessment Chart (PBAC), transfusion, blood products, thromboembolic events, and hysterectomy within 21 days; and mechanism of PPH reduction by VWF assays (VWF:RCo, VWF:Ag, VIII:C), fibrinogen, and d-dimer. Blood draws are at 5 time points, including at 32-39 weeks' gestation (screening), on admission for childbirth, and at 1 day, 2 days, and 21 days after delivery. The VWD-Woman Trial is considered greater than minimal risk as study drugs are given at delivery and special coagulation studies are obtained.

Principal Investigator: [name], DO

Co-Investigators: [name]

Protocol Title: The Von Willebrand WOMAN (VWD-Woman) Trial: A Phase III Randomized, Pilot Trial Comparing Recombinant von Willebrand Factor (rVWF, Vonvendi®) plus Tranexamic Acid (TA, Cyclokapron®) vs. rVWF, Vonvendi® alone to Prevent Postpartum Hemorrhage in Women with Von Willebrand Disease

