1.0 Objective and Specific Aims

The purpose of this 8-week single center, randomized, open-label pilot phase III trial is to prevent postpartum hemorrhage in women with von Willebrand disease. This 8-week open-label, randomized, controlled single-center trial will compare recombinant von Willebrand factor (rVWF, Vonvendi®) plus Tranexamic Acid (TA Cyclokapron®) vs. rVWF, Vonvendi® alone to reduce postpartum hemorrhage (PPH) in women with VWD. Both drugs are approved by the FDA to prevent and treat bleeding in individuals with von Willebrand disease. In this trial, subjects will be pregnant women age 18 years and older with VWD, defined as VWF:RCo <0.50 IU/dL and past bleeding history. The research is considered greater than minimal risk as it involves study drugs at delivery, and special coagulation studies are obtained. Blood loss at delivery will be by quantitative blood loss (QBL) at delivery calculated by a labor suite nurse, and postpartum blood loss will be lochial blood loss by pictorial blood assessment chart (PBAC), validated for postpartum blood loss. The primary endpoint is quantitative blood loss (QBL) during C-section and vaginal delivery and calculated by a labor suite nurse. The secondary endpoints will include i) assessment of safety by lochial blood loss by pictorial blood assessment chart (PBAC) validated for postpartum blood loss, transfusion, blood products, thromboembolic events, and hysterectomy within 21 days of delivery; and ii) assessment of the mechanism of PPH reduction by von Willebrand assays (VWF:RCo, VWF:Ag, FVIII:C), coagulation assays (fibrinogen, and d-dimer measured at screening (32-39 weeks') gestation (screening), on admission for childbirth, and at 1, 2, and 21 days postpartum. The trial will assess PPH hemorrhage reduction after each subject completes the 8-week trial.

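### The VWF:RCo threshold defining VWD is 0.50 IU/dL in inclusion criterion 2 and four other places, but 0.50 IU/ml (100 times higher) in the abstract

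*Combined protocol and SAP*

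**What the plan says.** The combined protocol and SAP defines von Willebrand disease by a VWF:RCo threshold and a bleeding history in six places. The number is 0.50 each time, but the unit is not always the same.

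- Section 4.3, inclusion criterion 2: "Confirmed VWD, as defined by VWF:RCo < 0.50 IU/dL and previous history of bleeding".
- Synopsis, Study Population: "defined by VWF:RCo <0.50 IU/dL (historic) and previous bleeding history".
- Section 1.0: "defined as VWF:RCo <0.50 IU/dL and past bleeding history".
- Section 4.1: "VWD will be defined as VWF:RCo < 0.50 IU/dL (historic) and previous history of bleeding".
- Section 4.5: "VWF:RCO < 0.50 IU/dL (historic) and a previous bleeding history".
- Abstract: "defined as VWF:RCo <0.50 IU/ml (historic) and previous bleeding history".

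Section 4.5 uses the definition to say who is eligible, adds that "Subjects approached for participation in this study will have VWD", and places the determination of eligibility before randomization and the first dose. It also requires every reason for exclusion to be documented.

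**The concern.** The threshold decides who enters the trial, and an error of unit in such a threshold is an error of scale. Five places give one cut-off and the abstract gives another that is far higher. The document has no conversion, no explanation and no statement of which unit is intended.

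A woman whose value falls between the two cut-offs has VWD by the abstract and does not have it by criterion 2. Staff who follow criterion 2 literally would exclude her. Staff who follow the abstract would enrol her in breach of the written criterion.

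Recruitment is one of the things this pilot is meant to test (sections 3.2 and 3.3). The count of women screened, excluded and enrolled can be interpreted only if the criterion behind it is clear. Section 4.5 also writes its eligibility sentence to cover "approximately 19 HTCs/obstetric hospitals (Phase III trial"), so the unit would carry over if that wording were reused.

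**Working it through.** No sample size, power or error rate depends on this threshold, so there is no statistical figure to reproduce. The check is a unit conversion and a comparison of the six definitions.

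**Inputs**

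| Place | Threshold as printed | In IU/dL | Marked *historic*? |
|---|---|---|---|
| Synopsis, Study Population | < 0.50 IU/dL | 0.50 | yes |
| Abstract | < 0.50 IU/ml | 50 | yes |
| Section 1.0 | < 0.50 IU/dL | 0.50 | no |
| Section 4.1 | < 0.50 IU/dL | 0.50 | yes |
| Section 4.3, criterion 2 | < 0.50 IU/dL | 0.50 | no |
| Section 4.5 | < 0.50 IU/dL | 0.50 | yes |

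**Conversion.** 1 dL = 100 ml, so:

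- 0.50 IU/ml × 100 ml/dL = 50 IU/dL
- 0.50 IU/dL ÷ 100 ml/dL = 0.005 IU/ml
- Ratio of thresholds: 50 ÷ 0.50 = 100

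**Where the definitions disagree**

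- Below 0.50 IU/dL: both are met.
- From 0.50 to just under 50 IU/dL: the abstract's is met, criterion 2 is not.
- 50 IU/dL and above: neither is met.

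The band of disagreement is 50 − 0.50 = 49.5 IU/dL wide.

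**Count.** IU/dL appears in 5 of the 6 definitions and IU/ml in 1.

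**Number of women affected.** The document gives no distribution of VWF:RCo, so this cannot be calculated. The only limits are the planned numbers: 20 enrolled (wrong inclusion) and up to 30 screened (wrong exclusion, section 3.2). The possible range is therefore everything from none to all, and no estimate is offered.

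**Side point.** The *historic* qualifier is in 4 of the 6 definitions and missing from section 1.0 and criterion 2. VWF:RCo is also measured at the screening visit, so criterion 2 as printed does not say whether the past or the screening value qualifies a woman.

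**The case against.** The best reply is that this is a typing slip with little practical consequence. The number is the same in all six places, which points to a wrong unit rather than two intended rules. Section 2.1 prints the same number and unit for a recommended level before epidural, which fits a habit of writing. The abstract and section 4.5 both defer to the inclusion and exclusion criteria, so criterion 2 governs and the abstract is only a summary. The trial runs at one specialist centre among women already under its care, where staff may never read the unit literally. The comparisons are descriptive, and the success and feasibility rules in section 3.3 do not use the threshold.

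Much of this stands. A slip is the likely cause, the harm depends on someone applying the text as written, and nothing in the document shows that anyone has been misclassified. The remark about later sites is conditional.

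The deference argument, however, does not remove the problem. It makes criterion 2 the operative rule without showing that criterion 2 carries the intended unit. If it does not, the governing text is the faulty one and four other places repeat the fault. Neither the majority of places nor the rank of the section settles what was meant. Sensible practice at the site also does not make the written criterion one that an auditor can check.

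**Conclusion.** The concern holds. The eligibility threshold is printed in two units that differ exactly 100-fold, the definitions conflict from 0.50 to just under 50 IU/dL, and no text reconciles them. The conversion needs no assumption. The practical harm assumes that at least one woman in that band is screened and that one of the two definitions is applied as printed.

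The effect is confined to eligibility, to what the screening log means, and to how the enrolled population is described. The sample size of 20, the dosing, the blood-loss endpoint and the descriptive analysis do not change. It should be fixed because the doubtful unit is in a numbered inclusion criterion, but it does not threaten the design.

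**What to change.** 1. The sponsor confirms the intended VWF:RCo threshold and states it once, in one unit, in the synopsis, the abstract and sections 1.0, 4.1, 4.3 (criterion 2) and 4.5. This review does not propose a value.
2. In the same edit, say whether the qualifying value is the historic one. If so, add that word to section 1.0 and criterion 2.
3. The sponsor checks the unit of the pre-epidural level in section 2.1 against its own sources. It repeats the same number and unit, but whether it is right cannot be judged from this document.

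The cost is a wording amendment. If women have already been screened or enrolled, their eligibility records and the screening log should be rechecked against the confirmed threshold. On the planned numbers that is at most 20 enrolled and 30 screened. No analysis has to be redone unless the recheck finds a woman who was wrongly enrolled.

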4.6 Risk/Benefit Assessment

Risk to Subjects

There are risks associated with the study drug and having blood drawn. rVWF and/or TA will be administered at delivery and on days 1 and 2 postpartum. All subjects will be asked to report any safety problems or side effects associated with administration of study drug(s).

Risk of Blood Draw

There may be discomfort with drawing blood, which is common, occurring in up to 25%, or 25 in 100 people: this may include pain, lightheadedness, fainting, bruising, or bleeding or infection in the tissue around the vein. This may be alleviated or reduced by applying pressure to the blood draw site for 5 minutes, and assuming a recumbent position, i.e. lying on your back with your head flat and knees bent, if lightheaded.

Risks of Study Drugs:

rVWF and TA

Allergic-type reactions are rarely reported for rVWF, at similar doses as in this study (e.g. 75 IU/kg), and thus, the risk is expected to be uncommon, occurring in < 0.001% or less than 1 in 100,000 people. Allergic reactions for TA are expected to be rare in this study, occurring in <.001%, or less than 1 in 100,000 people. Allergic reactions could include chills, fever, nausea and vomiting, or rarely may include, in decreasing order of severity, death, anaphylaxis (life-threatening difficulty breathing), low blood pressure, heartbeat irregularity, increase in body fluids, paresthesias (numbness or prickling sensation), urticaria (hives), chest tightness, rash, pruritus (itching), edema (swelling), fever, and/or chills. Should these symptoms occur, benadryl, a medication which reduces inflammation, may be given, with close monitoring of these symptoms. Benadryl may cause drowsiness, dizziness or low blood pressure. Subjects will be monitored for these symptoms. No one with a history of allergy (hypersensitivity), an allergic reaction or anaphylaxis associated with either recombinant von Willebrand factor (rVWF, Vonvendi®) or tranexamic acid (TA, Cyclokapron®) will be enrolled. Subjects will be monitored closely for early symptoms and signs of allergic or hypersensitivity reactions, including fever, chills, hives, tachycardia, chest discomfort, and anaphylaxis. Any subject who develops signs or symptoms of an allergic type reaction or anaphylaxis during administration of either study drug will immediately have that study drug stopped and appropriate medical care initiated.

Risk of Thromboembolism/Thrombogenicity

Although rVWF and TA may increase coagulation factor levels, they are rarely, if ever, associated with the development of thromboembolic complications. There is the unlikely possibility, < 0.001%, or less than 1 per 100,000 people, that either drug could cause a clot in the vein (thrombosis) with swelling or pain; or a clot in the lung (pulmonary embolus) with dyspnea or hemoptysis. Pregnancy is associated with increased risk of thromboembolism, but this is rarely seen in women with VWD: study drug will be limited to the first 2 days postpartum, per standard of care, as this is also the greatest time of postpartum bleeding. This risk will be very carefully monitored clinically. Should thrombosis symptoms occur measures considered standard of care would be

implemented to prevent clots: these include either compression stockings, which are support-like stockings, and/or sequential compression devices (SCDs). SCDs are blanket-like Velcro-devices which are placed on the legs to promote blood flow and prevent clots from forming in the leg veins. Should a clot occur, treatment would primarily consist of stopping the study treatment and/or removing the line in which it was given, if that is the source of the clot, as soon as possible. Should a bleeding episode occur during the study, the subject will be treated with rVWF or another hemostatic agent prescribed by the subject's physician.

Diphenhydramine (Benadryl)

Common Side Effects include sedation, sleepiness, dizziness, disturbed coordination, pain in the abdomen, and excess fluid or mucus.

Uncommon Side Effects include hives, rash, anaphylactic shock, sun sensitivity, excessive perspiration, chills, dryness of mouth, nose, and throat, low blood pressure, headache, rapid or irregular heartbeat, low blood cells, low white blood cell count, fatigue, confusion, restlessness, excitation, nervousness, tremor, irritability, insomnia, pins and needles feeling, blurred vision, double vision, a sensation of whirling and loss of balance (vertigo), ringing in the ears, inflammation of the inner ear ,nerve pain, convulsions, loss of appetite, nausea, vomiting, diarrhea, constipation, urinary frequency, difficult urination, urinary retention, early menses, tightness of chest or throat and wheezing, and nasal stuffiness.

Other Risks

Bleeding symptoms may occur in VWD unrelated to this study, usually with trauma, but sometimes spontaneously, without cause. Further, because individuals with VWD are enrolling on a trial in which study drug(s) will be administered by infusion, there is a risk of bleeding at the infusion site. Subjects should contact their physicians if this occurs and/or seek medical attention. In the event that bleeding at the infusion site cannot be stopped with pressure, it may be necessary to use a stitch or an adhesive material to stop the bleeding. The devices used to administer the stitch or adhesive may cause the following negative side effects: bleeding, a build-up of blood known as a hematoma, infection, allergic reaction, nerve injury, and swelling.

Risk of future testing of stored samples

Breach of confidentiality which could affect future insurability, employability, or reproduction plans, or have a negative impact on family relationships, and/or result in paternity suits or stigmatization. In order to reduce risks of disclosure or breach of confidentiality, the research related documents, blood samples and clinical information stored in subject research files will be assigned an alphanumeric (letters and numbers) identifier (that do not contain personal identifiers). For this study, a linkage key for linking this number and the subject's name will be kept at each site under lock and key by the PI and his/her research staff.

Collection of private health information and participant diary

There is also a potential for possible risk of breach of confidentiality of collected information. To minimize this risk, study participation and related information will be protected to maintain confidentiality. Blood samples and clinical history will be assigned an alphanumeric identifier and the key for linking this number with subject identity will be kept at each site under lock and key by the PI and his/her research staff. The de-identified information in this study will be placed into a secure, web-based data base at University of Pittsburgh Graduate School of Public Health (GSPH) Data Center. If the investigator publishes research information, subject names will not be identified.

Potential Benefits

The subjects will be under close supervision during the study period. After administration of rVWF or TA it is anticipated postpartum bleeding frequency will be decreased from the untreated state. For women with VWD, it is already established rVWF and TA may reduce postpartum bleeding, but whether one agent is more effective or better tolerated than the other is not known.

Risk Benefit Ratio

The risk/ benefit ratio indicates the value of the information to be gained outweighs the potential risks of participation in the trial as 1) risks associated with rVWF and TA are low, importantly thrombosis risk is <0.4% with VWF, based on data from the literature; and 2) individuals with cardiac disease, hypertension, MI, stroke, thrombosis, or seizure are excluded from the trial. Thus, the risk/benefit ratio of participating in the trial outweighs the risk of gained outweighs the potential risks of participation in the trial.

